## 10.2 Hypersensitivity

Induction of hypersensitivity to C19-A3 GNP will be assessed by a period of observation of subjects and during the immediate period after peptide injection. Local hypersensitivity may manifest as an increasing wheal and flare reaction at the site of peptide injection. The first patient dosed with GNP-peptide will be observed for 6 hours post dose – see section 7.3. Any adverse reactions will be communicated to the other trial treatment site by email, in addition to the standard pharmacovigilance procedures. Subsequent subjects will also be observed for 6 hours. If no serious adverse events are observed post first dose, subsequent visits will have an observation period of a minimum of 1 hour post dose, or 2 hours if there are any symptoms of signs of hypersensitivity. This time period has been chosen as the only anticipated severe reactions is one of hypersensitivity which, if systemic, would be apparent within 60 mins of intradermal dosing.

Observation will be by inspection of the injection site at 5 minute intervals for the first 15 minutes and then 15 minute intervals for a further 45 minutes. If any reaction is present and not resolving over this period, observation will be extended to 15 minute intervals until the reaction is reducing and < 1cm in diameter. Maximum size of any redness or swelling at the injection site will be recorded at each visit at which study drug is given (visits 1-3). Systemic hypersensitivity may manifest as shortness of breath; skin rash; tissue swelling; collapse. Subjects will be inspected for such signs at 5-minute intervals for the first 15 minutes and then at 15 minute intervals for a further 45 minutes. Pulse and blood pressure will be recorded at 15 minute intervals over this time. Any adverse events during this observation period will be recorded. To minimise any risk that might result from hypersensitivity:

- IMP administration should ONLY performed in a clinical research environment appropriate for phase 1 studies in which resuscitation facilities are immediately available.
- Facilities for treatment of a major hypersensitivity reaction, adrenaline, oxygen, intravenous infusion, head-down position, blood pressure and pulse monitoring should be available in the immediate environment of the subject, with access to hydrocortisone and antihistamines.
- Subjects should not be treated by a lone-worker unless he/she has immediate access to clinically trained support.
- Subjects should be directly observed for a minimum of 60 minutes after IMP administration and for up to an additional 2 hours or more if there are symptoms/signs of hypersensitivity.

There is an optional contact hypersensitivity testing or patch testing that can be performed anytime post final dose. This test was amended in per suggestion of the Data Steering Monitoring Board as a safety measure. This test determines delayed Type 4 hypersensitivity to allergens including gold for this study. This test can involve 3 visits (visit 2 is flexible and can be done at home) for the patient including day 0 (patches applied to back or arm of patient), day 2 (patches taken off and first reading- this can be done at home by the patient) and final reading (day 4 or day 7).

### **10.3 Disease exacerbation**

Laboratory tests for exacerbation of  $\beta$ -cell specific autoimmunity are (i) measurement of islet cell autoantibodies (against insulin, GAD-65, IA-2 and ZnT8) at 0 and 14 weeks; and (ii) measurement of pro-inflammatory  $\beta$ -cell specific T cell responses at 0, and 14 weeks. Clinical manifestation of disease exacerbation will be monitored by measurement of secreted C-peptide AUC after MMTT and stimulated urine c-peptide at 0 and 14 weeks ; HbA1c levels (0, 4, 8 and 14 weeks.); and the record of blood sugars and insulin use at each study visit. Disease specific quality of life questionnaires including hypoglycaemia fear (HFS), treatment satisfaction DTSQ and quality of life ADDQoL will be performed at 0 and 14 weeks.

## **11 ADVERSE EVENTS**

AE collection will be recorded from the time the participant receives their first dose of IMP until one month after the patient's last trial visit.

Adverse events will be monitored, reported in the trial publications and to the Trial Sponsor, Research Ethics Committee (REC), Medicines and Healthcare products Regulatory Agency (MHRA), Medical Products Agency (MPA) and the Regional Ethical Review Board in Linköping if appropriate.

Definitions used will be those under the Medicines for Human Use (Clinical Trials) Regulations 2004 and Amended Regulations 2006 as follows.

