**Table 1: Schedule of study visits**

Visit number	Screening		Pre V1	Treatment							Follow up				Optional	
	-2	-1		1	1b	1C	2	3	3b	3C	4	Pre V5	5	6	7	any time post dosing
Weeks	These visits can be combined. Treatment must start within 3 months of screening commencing 		A minimum of 72 hours prior to visit 1	0	1 day post visit1	3 to 5 days post visit 1	4	8	1 day post visit3	3 to 5 days post visit 3	9	A minimum of 72 hours prior to visit 5	14	20	52	
Days				0			28	56			63 (or one week post final injection)		98	140 (85 days post final dose)	366 (311 days post. final dose +/- 14 days)	
Informed consent	X															
Study drug administration				X			X	X								
Follow up telephone call 24 hours post IMP				X			X	X								
Physical Exam & ECG	X			X			X	X					X		X	
 Serum for AABs and immune markers				X							X		X		X	
DRB1*0401 genotype	X															
MMTT				X									X		X	
Photographs at injection site				X			X	X			X		X	X	X	
Blood sample to accompany skin studies (optional)								X								
Stitch removal from biopsy site (optional)										X						
urine or random serum c-peptide post meal		X		X									X		X	
72 hour continuous glucose monitoring			Attach CGM	X								Attach CGM	X		X	
Serum for Cystatin C				X							X		X	X	X	
Urinalysis for blood, protein, and beta-2 microglobulin		X		X			X				X		X	X	X	
Serum and urine (morning) sample to measure gold concentrations				X pre dose	X 				X 		X		X	X	X	
T cell (immune biomarker) assays (blood)				X				-			X		X		X	
 LN aspiration 0/3-5d				X		X		X		X						
 Safety blood samples		X		X			X				X		X	X	X	
HbA1c measurement		X		X			X				X		X		X	
Vital signs	X	X		X			X	X			X		X	X	X	
Adverse Event assessment/con meds		X	X	X	X	X	X	X	X	X	X	X	X	X	X	
Urine pregnancy test		X		X			X	X					X	X		
Record of insulin use	X			X			X	X					X		X	
 Blood glucose profile/insulin usage				X			X	X					X	X	X	

Assessment of glycaemic control/review blood sugar recordings				X				X	X					X		X	
Skin biopsy (optional) 																	X
Contact hypersensitivity testing (optional) 																	X
Suction blister (optional) 																	X
XHFS survey				X										X			
ADDQoL				X										X		X	
DTSQs				X										X		X	
DTSQc														X			

Screening can be up to 3 months

Treatment visits 1, 2 and 3 should be every 28 days +/- 3 days and follow up visit 5 should be at 14 weeks +/- 1 week

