### **6.10 Mechanistic immunological studies**

Mechanistic assessments will consist of:

- Ultra-sound guided Axillary LN aspiration and ELISPOT data before and 3-5days after administration of the first dose and the final dose of IMP (total of 4 aspirations for each patient)

- T cell assays to include enzyme-linked immunospot (ELISPOT) to measure T cell responses to PPI C19-A3 and other islet cell autoantigenic peptides using LN cells and fresh whole heparinised blood sent by courier to the assay laboratory
- Storage of peripheral blood mononuclear cells (PBMCs) for subsequent analysis of T cell responses (measurement of Tregs and antigen-specific T cells by tetramer and Diab-Q-kit)
- Storage of DNA for subsequent analysis of gene-phenotype interactions
- Storage of serum for islet autoantibody assessments and cell free DNA measurements
- Additional mechanistic assays by the T1D UK Consortium Mechanistic Core

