### **6.12 Ultrasound guided Fine Needle Aspiration of axillary lymph node**

Ultrasound guided Fine Needle Aspiration of axillary lymph node (US-guided FNA) will be performed by an experienced consultant radiologist, before and after Visits 1 and 3.

The procedure is as follows: Under aseptic technique and ultrasound guidance and following local anaesthetic, a 21G needle is inserted into an axillary lymph node and few drops of fluid aspirated and sent for immunological studies (as in section 6.10).

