## 10 PHARMACOVIGILANCE

### 10.1 Specification, timing and recording of safety parameters

The major associated safety parameters are evidence of induction of hypersensitivity and exacerbation of  $\beta$ -cell specific autoimmunity with accelerated  $\beta$ -cell loss. To address general safety concerns at screening and 0, 4, 8 and 14 weeks a physical examination will be conducted. A review of AEs will be performed at all visits and blood will be drawn at screening, weeks 4, 9, 14 & 20 to examine the full blood count; urea, electrolytes and creatinine; liver function tests; (prothrombin time, total bilirubin, total protein, albumin, AST (SGOT), SGPT (ALT), alkaline phosphatase; thyroid stimulating hormone; immunoglobulins (G, A, M); calcium; magnesium, phosphate, lipid profile (total cholesterol, LDL, HDL, triglyceride). Urinalysis for pH blood, protein, urine beta-2-microglobulin and albumin/creatinine ratio will be done at screening and visits 1, 2, 4, 5 and 6 and urine for cystatin-c will be collected at visits 1, 4, 5 & 6. A urine pregnancy test will be completed on females only, at all trial visits. At visits 1, 1b, 3b, 4, 5 and 6 blood and urine samples will be taken for gold concentrations to enable assessment of gold excretion. Laboratory measurements for these will be performed at the Midatech Pharma laboratory, Spain.

The safety of the investigational medicinal product (IMP) C19-A3 GNP has been extensively studied in pre-clinical toxicity studies. No signs of toxicity and no significant adverse effects in the organs and the >40 tissues examined were seen, not even at doses that were up to 500-fold higher than the intended dose in this clinical study, and given daily during 14 consecutive days. The studies revealed that the major organ of accumulation and excretion of the gold nanoparticles is the kidney, and to a much lesser extent the liver and spleen. Significant quantities of gold were only detectable in kidneys, which collected on average 30 % of the total dose administered (in rats) over the 14 day period, with a half-life of elimination of circa

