### **11.1 Definitions**

An Adverse Event (AE) is any untoward medical occurrence in a participant to whom an investigational medicinal product (IMP) has been administered, including occurrences which are not necessarily caused by or related to that product.

An Adverse Reaction (AR) is any untoward and unintended response, in a participant, to an IMP which is related to any dose administered to that participant. An Adverse Reaction is an Adverse Event with a causal relationship to the IMP.

Serious Adverse Event (SAE), Serious Adverse Reaction (SAR) or Serious Unexpected Suspected Adverse Reaction (SUSAR) is defined as an Adverse Event, Adverse Reaction or unexpected Adverse Reaction that:

- results in death;
- is life-threatening;  
The term “life-threatening” in the definition of serious refers to an event in which the participant was at risk of death at the time of the event; it does not refer to an event which hypothetically might have caused death if it were more severe;
- Requires hospitalisation or prolongation of existing hospitalisation. Hospitalization is defined as an inpatient admission, regardless of the length of stay, even if the hospitalization is a precautionary measure, for continued observation. Pre-planned hospitalisation e.g. for pre-existing conditions which have not worsened or elective procedures does not constitute an adverse event;
- results in persistent or significant disability or incapacity;
- consists of a congenital anomaly or birth defect; or
- is medically significant;  
Other events that may not result in death are not life-threatening, or do not require hospitalisation may be considered as a serious adverse event when, based upon appropriate medical judgement, the event may jeopardise the participant and may require medical or surgical intervention to prevent one of the outcomes listed above.

Pregnancy in either a participant or the partner of a participant taking trial medication will be recorded on a pregnancy notification form and the subject will be followed up until child birth.

A Suspected Unexpected Serious Adverse Reaction (SUSAR) is an adverse reaction that is both serious and unexpected.

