### 11.3 Principal Investigator/Trial Centre Responsibilities

The PI will be required to report all AEs/SAEs which occur during the Trial on an Adverse Event Form and keep a record in the case report form (CRF). AEs will be collected from the time the participant receives their first dose of IMP until one month after the last trial visit (visit 6, week 20). The AEs will be reported at agreed intervals to the DSMB and if there is any concern a DSMB meeting will be convened.

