5.1. Analysis of outcomes

5.1.1. Primary outcome

Assessment of the safety of C19-A3 GNP administration in terms of adverse events at the dose used is the primary outcome. This includes general safety concerns, induction of hypersensitivity and exacerbation of β -cell specific autoimmunity with accelerated β -cell loss. All enrolled patients will be included in the following analysis.

General Safety

To address general safety concerns at screening and 0, 4, 8 and 14 weeks a physical examination will be conducted. A review of AEs will be performed at all visits according to seriousness, causality and expectedness. Types of AEs, body systems involved and outcomes of the AE will be categorised and analysed by incidence per person dose used. All AEs will be collated

Hypersensitivity

Patients will be observed for local and systemic reactions post injection. Number of local reactions will be analysed by incidence per person dose used, size of the erythema note and time taken for erythema note size to be reduced to < 1 cm will be analysed by mean and standard deviation. Systemic reactions will be analysed by incidence per person dose used. Therapies used and outcome will be counted and reported.

Exacerbation of β -cell specific autoimmunity with accelerated β -cell loss

Differences between week 0 and 14 will be calculated for each patient and summarised by mean and standard deviations for the following parameters:

- Measurement of islet cell autoantibodies (against insulin, GAD-65, IA-2 and ZnT8)
- Measurement of pro-inflammatory β -cell specific T cell responses (analytes to be defined)

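### The protocol gives two different starting points for adverse event recording, and events caused by lymph node aspiration cannot be separated from the drug's all-cause incidence per person-dose

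*Protocol*

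**What the plan says.** **When recording starts.** Protocol section 11: "AE collection will be recorded from the time the participant receives their first dose of IMP". Section 11.3 repeats the rule: "AEs will be collected from the time the participant receives their first dose of IMP until one month after the last trial visit". The definition in section 11.1 fits it, since an AE is "any untoward medical occurrence in a participant to whom an investigational medicinal product (IMP) has been administered".

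**When AEs are reviewed.** The Table 1 row "Adverse Event assessment/con meds" is blank at visit -2 but marked at visit -1, Pre V1, visit 1 and every later scheduled visit. The SAP's Table 1 has the same pattern. Protocol 10.1: "A review of AEs will be performed at all visits". SAP 5.1.1: "A review of AEs will be performed at all visits according to seriousness, causality and expectedness".

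**The procedure.** Protocol 6.10 schedules node sampling "before and 3-5days after administration of the first dose and the final dose of IMP (total of 4 aspirations for each patient". Section 6.12 describes it: under local anaesthetic, "a 21G needle is inserted into an axillary lymph node and few drops of fluid aspirated".

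**Attribution and analysis.** Protocol 11.4 grades each AE on five levels for its relation to study treatment only. SAP Table 8, the AE data file, likewise has one relationship field, for the study drug. SAP 5.1.1 analyses AEs as incidence per person-dose and does not restrict this to treatment-emergent or drug-related events.

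**The concern.** Safety in terms of adverse events is the primary endpoint of a single-group, first-in-man study with no control arm. What counts as an event, and what it is attributed to, therefore carries most of the interpretation.

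Two things are unsettled. First, a site cannot follow both section 11 and Table 1 for an event found before dose 1. Section 11.1 builds serious adverse events on the AE definition, so a serious harm from the pre-dose aspiration is not formally a serious adverse event. It has no clear route into the 24-hour reporting in sections 11.4 and 11.5. Nor is it clear whether a patient who withdraws because of such a harm is analysed: SAP section 4 leaves out patients who withdraw before the first dose, while SAP 4.2 and 5.3 put all enrolled patients in the safety analysis.

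Second, after dosing, aspirations are as frequent as doses. Two of them come 3-5 days after an injection into the upper arm, in the node basin that drains it. A sore or swollen axilla at that point may be due to the needle or the drug, and the data file can express only the relation to the drug.

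**Working it through.** **Inputs.** 8 patients with 3 doses each (protocol 5.4). Aspirations before and after the first and final doses (protocol 6.10; SAP 5.1.2 names visits 1 and 3). Neither document gives an event rate per aspiration, so q is an assumption, taken over 2-25%.

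**Step 1: reproduce the stated count.** 2 doses × 2 time points = 4 aspirations per patient, as protocol 6.10 states.

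**Step 2: place the aspirations against the section 11 window.**
- All aspirations: 8 × 4 = 32
- Before dose 1, outside the window: 8 × 1 = 8 (25%)
- After dose 1, inside the window: 8 × 3 = 24 (75%)
- Person-doses: 8 × 3 = 24

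**Step 3: apply q.** Expected in-window events are 24q, which adds 24q / 24 = q to the incidence per person-dose. Expected events from the pre-dose aspiration are 8q. The chance of at least one of these, treating patients as independent, is 1 − (1 − q)^8.

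| Assumed q | In-window events, 24q | Added per person-dose | Pre-dose events, 8q | Chance of at least one pre-dose event |
|---|---|---|---|---|
| 2% | 0.48 | 0.02 | 0.16 | 15% |
| 5% | 1.2 | 0.05 | 0.40 | 34% |
| 10% | 2.4 | 0.10 | 0.80 | 57% |
| 20% | 4.8 | 0.20 | 1.60 | 83% |
| 25% | 6.0 | 0.25 | 2.0 | 90% |

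The pre-dose columns count every event from the first aspiration, whether or not it has resolved by the time of dosing. They are therefore an upper bound on events confined to the gap before the dose.

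**Step 4: can the planned fields separate these events?** In part. Table 8 holds AE start date and SAP Table 5 holds the date and time of administration, so an event on an earlier day can be identified as pre-dose. Table 8 lists no start time, and protocol Table 1 marks the first aspiration at visit 1, the dosing day. An event starting that day cannot be placed before or after the dose from these fields. No field identifies an event as caused by the aspiration.

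**The case against.** The case for leaving the plan alone has real content, and it rules out several stronger conclusions that a reader might draw.

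*Pre-dose harms are lost.* This would follow only if section 11 overrides Table 1, which neither document says. It concerns one aspiration in four. Bruising, soreness or infection that persists past the dose would be picked up at visits 1, 1b and 1C or at the 24-hour call. What stands is that the two rules conflict, and that the status of an event that began before the dose is undefined.

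*Procedure harms are automatically counted against the drug.* They are not. Section 11.4 has a not-related grade for events that another cause explains, and an all-cause count is not a statement of causation. What stands is that the event still enters the unrestricted incidence. Where needle and drug are equally plausible, the grade that fits is possibly related, with nowhere to record the competing cause.

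*There is no pre-dose comparator.* Table 1 has pre-dose AE checks. Physical examination, ECG, vital signs, safety bloods and urinalysis also have pre-dose values. The SAP is descriptive and plans no before-and-after comparison of AE rates, and a screening period of variable length, up to three months, would be a weak basis for one.

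*All 32 aspirations feed the AE table.* At q = 25% that would give 32 × 0.25 = 8 events, or 8 / 24 = 0.33 per person-dose. It requires pre-dose events to enter the numerator, which section 11 and the section 11.1 definition exclude. Under that window the figure is 24 aspirations and at most 6 events.

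*Table 1 already collects AEs from consent.* Consent is at visit -2, where the row is blank. The row is also shared with concomitant medication, so its visit -1 mark may refer partly to medication. Protocol 10.1 and SAP 5.1.1, however, speak of AEs alone.

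It is also fair to say that eight patients' events can be listed and read one by one. That eases interpretation but does not supply information the CRF never asked for.

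**Conclusion.** The point holds as an unreconciled recording rule and a missing attribution field. Sections 11, 11.1 and 11.3 conflict with Table 1, protocol 10.1 and SAP 5.1.1. For 8 of 32 planned aspirations, harm starting between procedure and dose has no consistent recording or serious-event reporting rule. For the other 24, any resulting AE adds to the primary all-cause incidence whatever its causality grade: about 0.5 to 6 events, or 0.02 to 0.25 per person-dose.

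The range rests on an assumed 2-25% event rate per aspiration, and on exactly eight patients completing three doses and four aspirations. Any replacement patient recruited after a missed dose would add to both counts. The interval between the first aspiration and dose 1 is not stated, so the number of events confined to that gap cannot be estimated. The documents do not show that events will be lost or that the drug will be blamed for them.

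**What to change.** 1. Reconcile protocol sections 11, 11.1 and 11.3 with Table 1 so that events are recorded from visit -1, or at the latest from the first trial procedure, each flagged as pre-dose or post-dose. State how a serious pre-dose event is reported.
2. Add a field for relation to trial procedure to section 11.4 and to SAP Table 8, alongside relation to study drug.
3. In SAP 5.1.1, compute incidence per person-dose on treatment-emergent events only. Tabulate pre-dose events and procedure-related events separately.
4. Align SAP section 4 with 4.2 and 5.3 on whether a patient who withdraws before dose 1 appears in the safety tables.

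The cost is one CRF field for procedure attribution, a pre-dose/post-dose flag, wording in both documents and a few more AE lines. No visit is added. If patients have already been treated, the new items would have to be completed from source notes for their events.

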### **11.1 Definitions**

An Adverse Event (AE) is any untoward medical occurrence in a participant to whom an investigational medicinal product (IMP) has been administered, including occurrences which are not necessarily caused by or related to that product.

An Adverse Reaction (AR) is any untoward and unintended response, in a participant, to an IMP which is related to any dose administered to that participant. An Adverse Reaction is an Adverse Event with a causal relationship to the IMP.

Serious Adverse Event (SAE), Serious Adverse Reaction (SAR) or Serious Unexpected Suspected Adverse Reaction (SUSAR) is defined as an Adverse Event, Adverse Reaction or unexpected Adverse Reaction that:

- results in death;
- is life-threatening;  
The term “life-threatening” in the definition of serious refers to an event in which the participant was at risk of death at the time of the event; it does not refer to an event which hypothetically might have caused death if it were more severe;
- Requires hospitalisation or prolongation of existing hospitalisation. Hospitalization is defined as an inpatient admission, regardless of the length of stay, even if the hospitalization is a precautionary measure, for continued observation. Pre-planned hospitalisation e.g. for pre-existing conditions which have not worsened or elective procedures does not constitute an adverse event;
- results in persistent or significant disability or incapacity;
- consists of a congenital anomaly or birth defect; or
- is medically significant;  
Other events that may not result in death are not life-threatening, or do not require hospitalisation may be considered as a serious adverse event when, based upon appropriate medical judgement, the event may jeopardise the participant and may require medical or surgical intervention to prevent one of the outcomes listed above.

Pregnancy in either a participant or the partner of a participant taking trial medication will be recorded on a pregnancy notification form and the subject will be followed up until child birth.

A Suspected Unexpected Serious Adverse Reaction (SUSAR) is an adverse reaction that is both serious and unexpected.

